### **12.1.5. 12-Lead Holter Monitor**

A Holter monitor will continuously record the patient's 12-lead ECG for a total of 72 hours from Day -1 (24 hours prior to the start of gene replacement therapy infusion) through 48 hours after the start of infusion. On Days -1 to Day 3, serial ECG data will be pulled in triplicate from the Holter monitor at the following time points:

- Pre-dose (within 24 hours prior to gene replacement therapy)
- 2 hours
- 4 hours
- 6 hours
- 8 hours
- 12 hours
- 24 hours
- 36 hours

- 48 hours

Twenty-four-hour Holter monitoring will also be performed at the 3, 6, 9, and 12-month visits and every 6 months thereafter. Twenty-four-hour Holter monitoring will also be performed at the End of Study visit when the patient reaches 18 months of age (or early termination). For patients enrolled in the study prior to amendment 3 and irrespective of study schedule, after signing an updated informed consent form, a 24-hour Holter monitor will be performed at the next scheduled visit and then in accordance with the Schedule of Assessments ([Appendix 5](#)).

Holter monitors will be provided to study sites along with a dedicated laptop for uploading the data from the memory cards for centralized review and analysis by a cardiologist within 24 hours of data upload. The Sponsor physician or designee will be notified of any safety concerns from the centralized review, and the safety management plan will be followed for documenting and reporting of AEs/SAEs.

#### **12.1.6. Echocardiogram**

A standard transthoracic echocardiogram will be performed at screening, at 3, 6, 9, and 12-month visits and every 6 months thereafter. An echocardiogram will also be performed at the End of Study visit when the patient reaches 18 months of age (or early termination) ([Appendix 5](#)). For patients enrolled in the study prior to amendment 3 and irrespective of study schedule, after signing an updated informed consent form, an echocardiogram will be performed at the next scheduled visit and then in accordance with the Schedule of Assessments ([Appendix 5](#)).

#### **12.1.7. Pulmonary Examinations**

Pulmonary examinations will be performed by a pulmonologist or appropriate individual as per standard institutional practice at each scheduled visit except Day 1 ([Appendix 5](#)). Prior to study entry, a pulmonologist or appropriate individual as per standard institutional practice will review and document ventilator usage in the 2 weeks prior to screening.

Patients may be fitted with non-invasive ventilatory support at the discretion of the pulmonologist or appropriate individual as per standard institutional practice and/or Investigator. Non-invasive ventilatory support equipment will be provided by AveXis through a third-party vendor. Should the patient require non-invasive ventilatory support at any time during the study, the equipment provided by AveXis must be used.

Patients requiring non-invasive ventilatory support will be asked to bring their machine(s) to each study visit such that the study staff can remove an SD card which captures actual usage data. The hours per day usage data for each day between visits will be extracted with software provided by the device manufacturer into a format that will be transferred/transcribed to the clinical database.

#### **12.1.8. Swallowing Test**

A swallowing test will be performed at screening (at the Investigator site), every 6 months starting at Month 6, and at End of Study when the patient reaches 18 months of age (or early termination) ([Appendix 5](#)) to determine if the patient has signs of aspiration. If the test is positive for aspiration, there may be a recommendation for the patient to use an alternate method

to oral feeding for the duration of the study at the determination of the Investigator and treating clinician.

#### **12.1.9. Photographs of Infusion Site**

Photographs will be taken of the infusion site at each scheduled visit from Day 1 (pre-dose) through Day 30 ([Appendix 5](#)) to monitor healing of the infusion site. AveXis will provide a secure and confidential upload process for transfer and storage of the photographs from the investigative sites to a contracted third-party vendor that will compile and arrange photographs as per AveXis requirements. Any/all photographs received at AveXis or the contracted vendor will be treated as confidential study data and will be the sole property of AveXis. AveXis and the contracted vendor will provide this secure, encrypted transfer and storage solution to properly protect the identities of patients/families in the photographs, which may be shared with regulatory agencies, the medical community, and/or in appropriate venues to discuss the results of this clinical study.

#### **12.1.10. Laboratory Assessments**

Blood samples will be collected at each scheduled visit, except Day 1 and Day 3 (as specified in [Appendix 5](#)). On Day -1, blood and urine samples will be processed locally for receipt of results prior to the start of gene replacement therapy infusion. Any clinically significant laboratory value will be repeated at the discretion of the Investigator.

In most instances, blood samples will be collected and shipped to a central laboratory, however, at the discretion of the Investigator, samples may be processed locally for emergent safety monitoring or other logistical or technical reasons that warrant samples to be processed locally. Samples for laboratory tests required during the in-patient vector infusion period prior to dosing will be collected and processed by the investigative site's Clinical Laboratory Improvement Amendment (CLIA) CLIA-certified local laboratory to ensure receipt of results prior to dosing.

**Table 6: Total Blood Volume**

Visit	Tests	Total Volume (mL)
Screening	Hematology, chemistry/CK-MB, virus serology, immunology sample (AAV9 Ab only), diagnostic confirmation sample	16.9
Day -1	Hematology, chemistry, capillary blood gas	3.3
Day 2	Hematology, chemistry, capillary blood gas	3.3
Day 7	Hematology, chemistry/CK-MB, immunology sample (ELISA/ELISpot)	7.6-9.6 b
Day 14	Hematology, chemistry, immunology sample (AAV9/SMN Ab only)	3.3
Day 21	Hematology, chemistry, immunology sample (AAV9/SMN Ab only)	3.3
Day 30	Hematology, chemistry/CK-MB, immunology sample (ELISA/ELISpot)	7.6-9.6 b
Day 60	Hematology, chemistry/CK-MB,	3.6
Month 3/4/5/7/8/10/11/13/14/16/17	Hematology, chemistry	25.3
Month 6/9/12/15	Hematology, chemistry/CK-MB	14.4
End of Study/ET	Hematology, chemistry/CK-MB	3.6
Maximum Total Volume for Studya		96.2

ET = early termination

a Patients will have different numbers of monthly visits, depending on their age at dosing. Maximum total volume based on a maximum of 16 monthly visits, provided T-cell responses are not elevated at Day 30 requiring additional surveillance samples and virus serology is not positive at screening requiring additional testing

b Immunology sample for IFN $\gamma$ - ELISpots requires 4-6 mL whole blood. Immunology sample for ELISA requires 1 mL whole blood. When drawn at the same visit, 4-6 mL is sufficient for both assays.

In a case where sufficient blood cannot be collected from a patient, blood will be used in the following priority order with the first having greatest priority and last having the least priority:

1. Safety labs
  - a. Chemistry
  - b. Hematology
  - c. CK-MB
2. Interferon gamma (IFN $\gamma$ ) ELISpots to detect -T-cell responses
3. Serum antibody to AAV9 and SMN
4. Genetic reconfirmation testing

If there is not sufficient blood volume to include the genetic reconfirmation testing sample at the screening visit, patient must return before Visit 2. All patients must have genetic reconfirmation testing completed.

#### 12.1.10.1. Hematology

Hematology analysis will include a complete blood count with differential and platelet count with smear. Samples will be collected and shipped in accordance with the laboratory manual

provided by the central laboratory. Blood samples for hematology analysis will be collected at all scheduled visits except Day 1 and Day 3 ([Appendix 5](#)).

Immediate/same-day hematology analyses required during in-patient dosing, as determined by the Investigator, will be performed as per investigational site standard procedures at the local laboratory. Investigators will receive hematology results from all study visits from the central laboratory.

#### **12.1.10.2. Blood Chemistry**

Samples will be collected and shipped in accordance with the laboratory manual provided by the central laboratory. Blood samples for chemistry analysis will be collected at all scheduled visits except Day 1 and Day 3 ([Appendix 5](#)).

Immediate/same-day chemistry analyses required during in-patient dosing, as determined by the Investigator, will be performed as per investigational site standard procedures at the local laboratory.

- Chemistry analysis will include the following at all study visits:
- Serum GGT
- AST/ALT
- Serum total bilirubin
- Direct bilirubin
- Albumin
- Glucose
- Total creatine kinase
- Creatinine
- BUN
- Electrolytes
- Alkaline phosphatase

Creatine kinase (CK-MB) will be collected at Screening, Day 7, Day 30, Day 60, Month 6, 9, 12, 15 months of age, and at 18 months of age/End of Study.

Investigators will receive chemistry results from all study visits from the central laboratory (except Day -1).

### **12.1.10.3. Urinalysis**

Urine samples will be collected in accordance with the laboratory manual provided by the central laboratory at all study visits except Day 1 and Day 3 ([Appendix 5](#)). Day -1 urinalysis will be performed as per investigational site standard procedures at the local laboratory. Urinalysis will include the following parameters:

- Color
- Clarity/turbidity
- pH
- Specific gravity
- Glucose
- Ketones
- Nitrites
- Leukocyte esterase
- Bilirubin
- Blood
- Protein
- Red Blood Cell
- White Blood Cell
- Squamous epithelial cells
- Casts
- Crystals
- Bacteria
- Yeast

### **12.1.10.4. Virus Serology**

The administration of an AAV vector has the risk of causing immune-mediated hepatitis. For patients who have HIV or positive serology for hepatitis B or C or Zika virus, administration of AAV vector may represent an unreasonable risk; therefore, negative serology testing must be confirmed at screening, prior to treatment. These samples will be collected at screening ([Appendix 5](#)) and shipped in accordance with the laboratory manual provided by the central laboratory.

### **12.1.10.5. Capillary Blood Gas**

Capillary blood gas will be completed locally at Day –1 and Day 2 ([Appendix 5](#)). A puncture or small incision will be made with a lancet or similar device into the cutaneous layer of the

patient's skin at a highly vascularized area (heel, finger, toe). To accelerate blood flow and reduce the difference between the arterial and venous gas pressures, the area will be warmed prior to the puncture. As the blood flows freely from the puncture site, the sample will be collected in a heparinized glass capillary tube.

#### **12.1.10.6. Immunology Testing (ELISA and IFN $\gamma$ - ELISpots)**

Blood samples for immunology testing will be collected and shipped to the central laboratory in accordance with the laboratory manual to test for serum antibodies to AAV9 and SMN (ELISA), and to perform IFN- $\gamma$  ELISpots to detect T-cell responses to AAV9 and SMN. Blood samples will be collected at screening (ELISA anti-AAV9 only), Day 7, Day 14 (ELISA anti-AAV9/SMN only), Day 21 (ELISA anti-AAV9/SMN only), and Day 30 ([Appendix 5](#)). Additional sampling may be performed at subsequent time points if ELISpot value(s) continue to be elevated, based on further discussion with the Principal Investigator and Medical Monitor.

#### **12.1.10.7. AAV9 Antibody Screen in Mother**

There is potential that the biological mother of the patient may have pre-existing antibodies to AAV9 that may be transferred to the patient through breast milk or, theoretically, via placental transfer in utero. Informed consent will be requested from the biological mother of the patient to screen the mother for circulating antibodies to AAV9. Once informed consent has been obtained, the mother will have her blood drawn from a peripheral vein at screening and shipped to the central laboratory for screening of anti-AAV9 antibodies. Mothers who test positive for antibodies to AAV9 will be asked to refrain from further feedings with breast milk.

If AAV9 antibodies are identified, the patient must desist in consuming breast milk from the biological mother.

Patients consuming banked breast milk from donor sources that cannot be test for anti-AAV9 antibodies must be transitioned to formula prior to participation.

#### **12.1.10.8. Blood for Diagnostic Confirmation Testing**

A blood sample will be collected during the screening visit and shipped to the central laboratory in accordance with the laboratory manual for reconfirmation of *SMN1* deletions/mutations, *SMN2* copy number, and absence of exon 7 gene modifier mutation (c.859G>C). This will be done to ensure consistency in diagnostic testing practices.

#### **12.1.10.9. Saliva, Urine, and Stool Collection**

Studies have shown that some vector can be excreted from the body for up to a few weeks after injection; this is called "viral shedding." Vector shedding can be found in the blood, urine, saliva, and stool for up to 1 week following infusion. The potential health risks associated with the shed vector are not fully known at this time; however, the health risk is thought to be low as the vector cannot replicate. Regardless, Institutional Review Board (IRB)/Independent Ethics Committee (IEC)-approved instructions should be provided to the patient's family and care giver(s) regarding use of protective gloves if/when they come into direct contact with the patient's bodily fluids and/or waste, as well as good hand-hygiene for a minimum of 2 weeks (14 days) after gene replacement therapy. Additionally, patients are prohibited from donating blood for 2 years following the vector infusion.

Saliva, urine, and stool samples will be collected for viral shedding studies at screening, 24 hours postdose-, 48 hours post-dose, Day 7, Day 14, Day 21, and Day 30 ([Appendix 5](#)). Samples will be collected, prepared, and shipped as per the laboratory manual.

A subset of patients at sites opting to participate in the viral shedding sub-study will have 24-hour total volume urine and fecal samples collected through 24 hour post-dose and through 48 hours-post dose.

## 13. ADVERSE AND SERIOUS ADVERSE EVENTS

### 13.1.1. Definition of Adverse Events

#### 13.1.1.1. Adverse Event

An AE is the development of an undesirable medical condition or the deterioration of a pre-existing medical condition following or during exposure to a pharmaceutical product, whether or not considered casually related to the product. In clinical studies, an AE can include an undesirable medical condition occurring at any time, including baseline or washout periods, even if no study treatment has been administered.

All adverse events that occur from the start of gene replacement therapy infusion through the last study visit will be collected and recorded in the eCRF.

All adverse events will be classified in accordance with the CTCAE version 4.03 outlined in [Table 7](#).

**Table 7: Common Terminology Criteria for Adverse Events**

Grade	Definition
1	Mild; asymptomatic or mild symptoms; clinical or diagnostic observations only; intervention not indicated
2	Moderate; minimal, local or noninvasive intervention indicated; limiting age-appropriate instrumental ADL. a
3	Severe or medically significant, but not immediately life-threatening; hospitalization or prolongation of hospitalization indicated; disabling; limiting selfcare -ADL. b
4	Life-threatening consequences; urgent intervention indicated.
5	Death related to AE.

Source: Common Terminology Criteria for Adverse Events (version 4.03) [9]

a Instrumental ADL refer to preparing meals, shopping for groceries or clothes, using the telephone, managing money, etc.

b Self-care ADL refer to bathing, dressing and undressing, feeding self, using the toilet, taking medications, and not bedridden.

Study enrollment will be interrupted should any patient experience an unanticipated CTCAE Grade 3, or higher adverse event toxicity that is possibly, probably, or definitely related to the gene replacement therapy. The event will then be reviewed by the DSMB and an evaluation will be made as to whether the study should be terminated early following the discontinuation rules.

Unanticipated CTCAE Grade 3 or higher adverse events that are possibly, probably, or definitely related to the gene replacement therapy must be reported within 24 hours to Sponsor and/or designee as per study safety management plan to ensure timely escalation to the DSMB.

### **13.1.1.2. Serious Adverse Event**

A SAE is an AE occurring during any study phase (e.g., baseline, treatment, washout, or follow-up), and at any dose of the investigational product, or comparator that fulfills 1 or more of the following:

- Results in death
- It is immediately life-threatening
- It requires in-patient hospitalization or prolongation of existing hospitalization
- Results in persistent or significant disability or incapacity
- Results in a congenital abnormality or birth defect
- It is an important medical event that may jeopardize the patient or may require medical intervention to prevent 1 of the outcomes listed above.

All SAEs that occur after signing of the informed consent through the last study visit, whether or not they are related to the study product, must be collected and recorded on forms provided by the Contract Research Organization.

### **13.1.1.3. Other Adverse Event**

The following specific treatment-emergent AE of special interest, which may be searched using Standardized Medical Dictionary for Regulatory Activities (MedDRA) queries, will be summarized:

- Elevated liver enzymes

Other adverse events (OAE) will be identified by the Drug Safety Physician and, if applicable, also by the Clinical Study Team Physician during the evaluation of safety data for the Clinical Study Report. Significant adverse events of particular clinical importance, other than SAEs and those AEs leading to discontinuation of the patient from the study, will be classified as OAEs. For each OAE, a narrative may be written and included in the Clinical Study Report.

## **13.2. Relationship to Study Product**

An Investigator who is qualified in medicine must make the determination of relationship to the investigational product for each AE (Unrelated, Possibly Related, Probably Related, or Definitely Related). The Investigator should decide whether, in his or her medical judgment, there is a reasonable possibility that the event may have been caused by the investigational product. If no valid reason exists for suggesting a relationship, then the AE should be classified as “unrelated.” If there is any valid reason, even if undetermined, for suspecting a possible cause-and-effect relationship between the investigational product and the occurrence of the AE, then the AE should be considered “related.”

If the relationship between the AE/SAE and the investigational product is determined to be “possible” or “probable” then the event will be considered related to the investigational product for the purposes of expedited regulatory reporting.

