#### 9.2.1. Prophylactic Administration of Prednisolone

An antigen specific T-cell response to the AAV vector was observed in the ongoing Phase 1 clinical study (AVXS-101-CL-101) investigating AVXS-101 treatment via IV infusion. This is an expected response between 2 to 4 weeks following gene replacement therapy. One possible consequence to such antigen specific T-cell response is clearance of the transduced cells and loss of transgene expression.

In an attempt to dampen the host immune response to the AAV based- therapy, all patients will receive prophylactic prednisolone at approximately 1 mg/kg/day beginning 24 hours prior to gene replacement therapy until at least 30 days post-infusion. After 30 days of treatment, the dose of prednisolone can be tapered for patients whose ALT values, AST values, and T-cell

response are  $\leq 2 \times$  ULN for ALT and AST, and  $< 100$  SFC/ $10^6$  PBMCs in accordance with the following treatment guideline:

- Until at least 30 days post-infusion: 1 mg/kg/day
- Weeks 5 and 6: 0.5 mg/kg/day
- Weeks 7 and 8: 0.25 mg/kg/day
- Week 9: prednisolone discontinued

If the AST or ALT values are  $> 2 \times$  ULN, or if T-cell response is  $\geq 100$  SFC/ $10^6$  PBMCs after 30 days of treatment, the dose of prednisolone will be maintained until the AST and ALT values decrease below threshold. If T-cell- response continues past Day 60, Investigator discretion should be used considering risk benefit for maintaining prednisolone. Variance from these recommendations will be at the discretion of the Investigator based on potential safety issues for each patient.

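### Causality is rated against AVXS-101 only, so adverse events attributed solely to the protocol-mandated prednisolone are recorded as unrelated and cannot be identified in the causality data

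*Protocol*

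**What the plan says.** The file holds protocol versions 4.0 and 3.0; on the sections quoted here they agree.

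- **Causality (Section 13.2).** "An Investigator who is qualified in medicine must make the determination of relationship to the investigational product for each AE". Where the investigator sees no ground for suspicion, "If no valid reason exists for suggesting a relationship, then the AE should be classified as" unrelated. The threshold for the opposite answer is low: "If there is any valid reason, even if undetermined, for suspecting a possible" causal link to the investigational product makes the event related. Table 5 and Section 10.1 name AVXS-101 as the only product.
- **Prednisolone (Section 9.2.1).** "all patients will receive prophylactic prednisolone at approximately 1 mg/kg/day beginning 24 hours prior to gene replacement therapy until at least 30 days post-infusion". The dose then tapers through Week 8, and the guideline closes with "Week 9: prednisolone discontinued". The full dose is kept longer if liver enzymes or T-cell response stay above threshold.
- **Collection window (Section 13.1.1.1, repeated in Section 13.3 and in footnote n of Appendix 5).** "All adverse events that occur from the start of gene replacement therapy infusion through the last study visit will be collected". Serious events are collected from signed consent, whatever their relationship to the product (Section 13.1.1.2).
- **Triggers.** In the text after Table 7 in Section 13.1.1.1, "Study enrollment will be interrupted should any patient experience an unanticipated CTCAE Grade 3, or higher adverse event toxicity", provided it is at least possibly related to the gene replacement therapy. The unacceptable-toxicity criterion in Section 7.3 and the main ad hoc DSMB trigger in Section 15 carry the same condition.

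**The concern.** AVXS-101 is never given in this trial without prednisolone. The steroid is mandated for every patient, has its own row in the Schedule of Assessments from Day -1, and is recognised as a source of risk: hypersensitivity to it is exclusion criterion 10. Yet no section asks whether an event is due to it.

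There is no concurrent control arm, so the investigator's attribution is one of the few sources of information on where an event came from. With a single causality field, an infection or metabolic event that the investigator blames wholly on the steroid gets the same code as an event blamed on spinal muscular atrophy or on chance. A table of related events then understates the harm attributed to the regimen as given, and no table built on the causality field can recover it.

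The same code decides whether the immediate safety steps start. Section 6.4 defines unacceptable toxicity as treatment-related, but the protocol does not say whether treatment there, or gene replacement therapy in the triggers, includes the required steroid.

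**Working it through.** The protocol gives no figure to reproduce. The check sets the passages side by side, with one small calculation.

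**1. Follow one event attributed only to prednisolone.**

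| Step | Provision | Outcome |
|---|---|---|
| Causality | 13.2: rated against AVXS-101 only | Unrelated |
| Enrollment interruption and 24-hour escalation of Grade 3 or higher events | 13.1.1.1: needs relation to gene replacement therapy | Not met |
| Unacceptable toxicity | 7.3: same condition | Not met |
| Ad hoc DSMB meeting, main trigger | 15: same condition | Not met |
| Quarterly DSMB review | 15: all safety data, no relatedness filter | Included |
| DSMB recommendation to terminate | 7.3: for safety reasons, no relatedness condition | Available |
| Serious event reporting | 13.4: within 24 hours, related or not | Applies if serious |
| Grade 3 or higher endpoint | 14.1.1.4: no causality condition | Counted |

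The steps that fail are those that use the causality field. The others work without it.

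**2. Follow an event where AVXS-101 and prednisolone are both suspected.** Any valid reason to suspect AVXS-101 makes it related under Section 13.2, and the relatedness condition of each trigger is met. The problem is therefore confined to events attributed to the steroid exclusively.

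**3. Size of the collection gap.** Inputs: first dose 24 hours before infusion and guideline course through Week 8 (Section 9.2.1); collection of all adverse events from infusion (Section 13.1.1.1).

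- Guideline course: 1 + 8 × 7 = 57 days. Share before collection starts: 1/57 = 1.8%.
- Minimum full-dose period only: 1 + 30 = 31 days. Share: 1/31 = 3.2%.

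The 57 days are not a ceiling, because the dose can be maintained beyond the guideline; a longer course makes the share smaller. Only non-serious events fall in this gap.

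**4. What remains for non-serious events.** Section 13.3 notes that a severe event need not be serious. A non-serious Grade 3 event attributed only to prednisolone has no 24-hour route to the sponsor under Section 13.1.1.1 or 13.4. Its scheduled DSMB review is the next quarterly meeting, which may be up to about three months away.

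**The case against.** The strongest reply is that the safety net is wider than the causality field. A reader might infer that steroid harm escapes every toxicity trigger and receives no review. The documents do not support that. The DSMB sees all serious and other adverse events each quarter and may recommend suspension, modification or discontinuation. Serious events go to the sponsor within 24 hours whatever their cause. The Grade 3 or higher endpoint has no causality filter. The ad hoc clause in Section 15 also names any patient death and important laboratory findings, although it can be read as limited to events attributed to the gene replacement therapy. All of this stands.

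A reader might also infer that harm on Day -1 goes unrecorded. It does not if it is serious, and many severe infections or metabolic events would be serious through hospitalization. On that day the infant is in hospital with vital signs, laboratory tests and a pulmonary examination scheduled. Nor is there a contradiction in Section 13.1.1.1: its remark that adverse events can occur in baseline periods is a general definition, and the next paragraph sets this study's window.

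Further points stand. The triggers also require an event to be unanticipated, a word the protocol does not define, so recognised steroid effects might stay outside them even if the relatedness wording covered prednisolone. A second field records attribution; it cannot remove the confounding when every patient receives both products. The safety management plan and the DSMB Charter are not shown and might address prednisolone.

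None of this supplies the missing attribution. Section 13.2 fixes the causality question for each event, and the provisions listed do not mark which unrelated events were attributed to the steroid.

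**Conclusion.** The point holds in limited form. Section 13.2 leaves an event attributed solely to the mandated prednisolone indistinguishable, in the causality data, from one due to disease or chance. It affects every patient (up to 20) throughout the steroid course, 57 days on the guideline taper and longer where the dose is maintained. The documents give no rate for such events, so their number cannot be estimated.

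The consequence for the triggers is real but partial: only those that depend on relatedness are missed, and only by events where AVXS-101 is not suspected at all. The collection gap is minor, at about 1.8% of the guideline course and non-serious events only.

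The conclusion assumes that investigators apply Section 13.2 as written and that no unseen document adds a prednisolone attribution. It does not extend to saying that the enrollment pause or the termination criterion should be widened. That would change a stopping rule, and no contradiction in the protocol requires it.

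**What to change.** - **Section 13.2:** add a second causality assessment, for the protocol-required prednisolone, and tabulate adverse events by it alongside the AVXS-101 assessment.
- **Sections 13.1.1.1 and 13.3, and footnote n of Appendix 5:** start collection of all adverse events at the first prednisolone dose.
- **Sections 7.3, 13.1.1.1 and 15:** the sponsor should state whether relation to gene replacement therapy is meant to cover the mandated regimen or AVXS-101 alone. This is a request to clarify the existing wording; no new stopping rule is proposed.

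The cost is one eCRF field, one extra day of adverse event collection per patient and amendment wording. Doses, visits and the efficacy analysis do not change.
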